3.8.2 Deaths

Deaths will be listed from the Death Report form showing date and cause of death.

3.9 Laboratory Evaluations

Conversion factors will be applied where needed to report all laboratory results in International System of Units (SI) units. Global reference ranges will be used to aid interpretation of the laboratory data.

Laboratory parameters will be listed in the following order:

- Haematology: haematocrit, haemoglobin, platelet count, erythrocyte count, white blood cell count, absolute neutrophils, absolute lymphocytes, absolute monocytes, absolute eosinophils, absolute basophils, lymphocyte subsets.
- Serum biochemistry: sodium, potassium, calcium, creatinine, uric acid, alkaline phosphatase (total ALP), aspartate aminotransferase (ASAT), alanine aminotransferase (ALAT), LDH, Gamma Glutamyl Transferase (γ GT), glucose, bilirubin (total), albumin, immunoglobulin levels.
- Coagulation.

Haematology, biochemistry and coagulation data will be listed separately including global reference ranges, with flags to indicate all out of range values.

Blood urea nitrogen (BUN) and urea will not be listed due to quality concerns. This was due to confusion at sites when collecting the data and it is not possible to correct these issues retrospectively. No concerns were raised regarding renal function during the trial and no signals were seen when reviewing the raw data.

3.9.1 Summaries of Numeric Laboratory Results

- Study baseline and Betalutin baseline values for the following laboratory parameters: Neutrophils, Lymphocytes and Platelets.
- Only data from day 0/1 to day 92 will be included in any summary tables and plots.
- Values at each post-study baseline analysis window (scheduled visit) for all laboratory parameters.
- Change from Betalutin baseline at each post-baseline analysis window (scheduled visit) for all laboratory parameters.

A summary table will be produced for neutrophil, lymphocytes and platelet counts, by dose regimen and overall. This will include the following:

Neutrophil count

- Number (%) participants with neutrophil count $< 1 \times 10^9/L$ at any time post-Betalutin baseline (where $1 \times 10^9/L = 1\ 000/mm^3$)
- Number (%) participants with neutrophil count $< 0.5 \times 10^9/L$ at any time post-Betalutin baseline (where $0.5 \times 10^9/L = 500/mm^3$)

Platelet count will be presented in an analogous method to neutrophil count but using the following thresholds:

- platelet count $< 50 \times 10^9/L$ (where $50 \times 10^9/L = 50\ 000/mm^3$)
- platelet count $< 25 \times 10^9/L$ (where $25 \times 10^9/L = 25\ 000/mm^3$)

Lymphocyte counts will be presented in an analogous method to neutrophil count but using the following thresholds:

- Lymphocyte count $< 0.2 \times 10^9/L$ (where $0.2 \times 10^9/L = 200/mm^3$)

Mean haematological data, for each dose regimen, will be plotted for neutrophil count, platelet counts, lymphocytes, and possibly other parameters based on results. Change from baseline plots will not be produced.

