9.4 Supportive Care Guidelines

Persistent neutropenia (neutrophils/granulocytes $< 0.5 \times 10^9/L$) without fever

Patients with persistent neutropenia will be started on G-CSF 5 µg/kg/daily given subcutaneous until the neutrophil count has reached the local hospital’s reference range.

Neutropenia with fever (Neutrophils/granulocytes $< 1 \times 10^9/L$; fever $> 38^\circ C$)

Blood cultures will be obtained from the patient. The patient should start on empiric antibiotics as long as clinically indicated. Provision of G-CSF to such patients is highly recommended.

Severe thrombocytopenia (platelets $< 5 \times 10^9/L$) or bleeding with platelets $< 50 \times 10^9/L$

Patients will be transfused with platelets to maintain a platelet count $> 20 \times 10^9/L$ or higher if clinically indicated to control bleeding. Epsilon aminocaproic acid may be given to patients with mucosal bleeding and platelet count $< 50 \times 10^9/L$.

Severe anaemia (haemoglobin < 8.0 g/dL)

Patients will be transfused with packed red cells to maintain haemoglobin level > 8.0 g/dL.

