13.1 Adverse Events: Definitions

13.1.1 Definition of Adverse Event

An AE is defined as the appearance of (or worsening of any pre-existing) undesirable sign(s), symptom(s) or medical condition(s) that occur after the patient’s signed informed consent has been obtained.

An AE can be any unfavourable and unintended sign (including an abnormal laboratory finding), symptom, or disease temporally associated with the use of an IMP, whether or not considered related to the IMP.

Abnormal laboratory values or test results occurring after informed consent constitute AEs only if they:

- induce clinical signs or symptoms, or
- are considered clinically significant, or
- require therapy (e.g. transfusion) or
- require changes in medications.

Laboratory abnormalities that meet the criteria for AE should be followed until they have returned to normal. Laboratory abnormalities not requiring clinical intervention or further investigation will be captured as part of overall laboratory monitoring, and should not be reported as adverse events.

Progression of underlying malignancy should not be reported as an AE, unless the investigator considers that the study drugs contributed to lymphoma progression (by a means other than lack of effect). AEs separate from the progression of malignancy (e.g. deep venous thrombosis

at the time of progression) should be reported as per usual guidelines with proper attribution regarding relatedness to study treatment.

Each event will be evaluated by the investigator for clinical significance, severity and CTCAE grading, and should be recorded in the eCRF. AEs will be assessed according to the CTCAE Version 4.0 or later as applicable. The following information should be recorded:

- Whether the event is serious or non-serious
- Relationship to study drug
- Severity of the event
- Onset date and time
- Resolution date and time, or date and time of death
- Action taken
- Outcome of the event

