13.4.5 Clinical Laboratory Parameters

Blood samples for the determination of biochemistry and haematology parameters will be drawn at pre-specified time points, see Schedule of Assessments, Table 6-5, Table 6-7 and Table 6-8 (Section 6.3).

The following laboratory tests will be performed:

Table 13-2 Clinical Laboratory Parameters

Serum Biochemistry	Haematology
Sodium	Haematocrit
Potassium	Haemoglobin
Calcium	Platelets
Creatinine	Red blood cell count
Uric acid	White blood cell count
Urea	Differential
Alkaline Phosphatase (total ALP)	Neutrophils
Aspartate aminotransferase (AST)	Lymphocytes
Alanine aminotransferase (ALT)	Monocytes
Lactate Dehydrogenase (LDH)	Eosinophils
Gamma glutamyl transferase	Basophils
Glucose	Lymphocyte subsets
Bilirubin, total	HAMA test
Albumin	Coagulation – PT/INR and PTT (only Part B and Part C)
Protein electrophoresis (gamma globulin g/L)*	
Quantitative serum immunoglobulins (IgG, IgA and IgM)	

Serum Biochemistry	Haematology
HIV test (only Part B and Part C)*	
Hepatitis C (only Part B and Part C)*	
β-HCG (pregnancy test)**	
Hepatitis B test (HBsAg and anti-HBc)*	

*At screening only

**At screening only; post-dose urine pregnancy tests will also be performed in Parts B and C

Reference ranges from the laboratory will be provided to the Sponsor. If during the study, ranges should be changed, the investigator is requested to provide updated laboratory normal values.

The investigator will interpret all clinical laboratory test results outside the reference range.

Laboratory values outside reference range recorded in the CTCAE, will be graded 1 to 4 according to the CTCAE criteria. The laboratory CTCAE grade will be derived programmatically for the purpose of reporting in the Clinical Study Report.

Investigators will assess abnormal laboratory values or test results occurring after informed consent. Abnormal laboratory results constitute AEs only if they:

- induce clinical signs or symptoms, or
- are considered clinically significant, or
- require therapy (e.g. transfusion) or
- require changes in medications.

Laboratory abnormalities that meet the criteria for AE should be followed until they have returned to normal. Laboratory abnormalities not requiring clinical intervention or further investigation will be captured as part of overall laboratory monitoring, and should not be reported as AEs.

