14.1.10 Analysis of Safety Data

Standard safety listings will be provided for treatment exposure, patient disposition, AEs, AEs leading to discontinuation, SAEs, laboratory safety data (serum chemistry and haematology), vital signs, 12-lead ECG, physical examination, ECOG performance status, and long-term toxicity. i.e. all safety parameters mention in [Section 13](#).

The incidence of AEs will be tabulated and reviewed for potential significance and clinical importance. The number of patients reporting AEs, and the number of AEs reported will be presented. AEs will be coded using MedDRA and graded according to CTCAE. The events will be tabulated by system organ class, preferred term, CTCAE grading, severity, and relationship to study medication. Start of AE after study medication injection and duration of AEs will also be tabulated. SAEs will also be presented in separate tabulations.

For laboratory data, the number of abnormal and clinically significant observations will be listed by patient and by time of measurement. The laboratory values will also be graded according to toxicity graded as CTCAE. All patients who receive any amount of the study

medication will be evaluated for toxicity.

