Category	Data	Comments
Demography and baseline information	Demographics	
	Disposition	
	Eligibility	Includes reasons for screening failure
	Med history	diagnosis of NHL (part C patients)
	Med history	diagnosis of FL (part B patients)
	Med history	general med history, listing only, no summaries required
	Prior and con meds	Prior meds, listing only, no summaries required
	Prior and con meds	Previous treatment for FL (part B), iNHL (part C)
Efficacy endpoints to be summarised are: ORR, CRR, DoR, DoCR and PFS from IRC assessment	Tumour visit response	From IRC: ORR, CRR, DoR, DoCR, PFS
Exposure data	Exposure	
Safety (AE and laboratory data) data	AE	
	Biochem	Listings only, no summaries required

	Haematology	Both listings and summaries required
--	-------------	--------------------------------------

OS variables will not be derived.

For all other data no formal TFL outputs are required. For all data in the table below, SAS datasets of the raw data should be supplied to Nordic Nanovector.

Table 2: Data for which only SAS raw data sets are required

Data table	Comments
AE SI	
Dna damage	DNA damage (Date/time) is this available?
ECG	ECG data only collected at baseline
Genomic biomarkers	Sample collection for genomic biomarkers
Imaging	Spect/CT evaluation
Immunological assessment	Protein Electrophoresis
Lab test results	Pregnancy test
Phys exam	Physical exam at baseline and through trial
PK concentrations	PK sampling times
Prior and con meds	Previous treatment for iNHL
Prior and con meds	Further anti-cancer therapies
Prior and con meds	Concomitant medications
Prior and con procedures	
Questionnaire	ECOG
Questionnaire	FACT-Lym
Response	Response following CT and PET assessments
SAE	
Serology sample	Sample collection for serology, hep B hep C HIV
Subject characteristics	Confirms randomisation and dose
Tumour identification	Biopsy tumour tissue - sample date, site, slides
Tumour identification	Target lesions (screening & follow-up)
Tumour identification	Non-measurable lesions (screening & follow-up)
Tumour identification	New lesions
Tumour identification	Bone marrow (screening & follow-up)
Tumour identification	PET (screening & follow-up)
Vital signs	Screening & follow-up
Immunological assessment	ADA (Date/time of sample)

Immunological assessment	HAMA (Date/time of sample)
Immunological assessment	Immunoglobulin (Date/time of sample)
Immunological assessment	Lymphocyte (Date/time of sample)

2 Study Design, Objectives and Endpoints

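### The SAP omits the protocol's programmatic CTCAE grading of laboratory values, so outside three cell counts the incidence of laboratory toxicity rests on adverse event reporting alone

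*SAP*

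**What the plan says.** **Protocol.** Section 13.4.5 assigns grades 1 to 4 to out-of-range values that CTCAE covers, and adds: "The laboratory CTCAE grade will be derived programmatically for the purpose of reporting in the Clinical Study Report". Section 14.1.10 repeats it: "The laboratory values will also be graded according to toxicity graded as CTCAE". Sections 13.1.1 and 13.4.5 also say which laboratory abnormalities are adverse events: those that cause signs or symptoms, are judged clinically significant, need treatment (transfusion is the example given) or lead to a change in medication. For the rest, "Laboratory abnormalities not requiring clinical intervention or further investigation will be captured as part of overall laboratory monitoring", and they are not reported as adverse events. Section 14.1.5 says the SAP will record any change to the protocol's analyses.

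**SAP.** Laboratory data stay in the safety objective (2.2) and among the safety endpoints (2.3). Table 1 gives biochemistry "Listings only, no summaries required" and haematology "Both listings and summaries required". Section 3.9 lists results with out-of-range flags against global reference ranges. Section 3.9.1 plans by-visit values and "Change from Betalutin baseline at each post-baseline analysis window (scheduled visit) for all laboratory parameters". It then adds the count table: "A summary table will be produced for neutrophil, lymphocytes and platelet counts, by dose regimen and overall". The cut-offs, all ×10⁹/L, are below 1 and 0.5 for neutrophils, below 50 and 25 for platelets, and below 0.2 for lymphocytes. CTCAE grade appears only for adverse events (3.8.1 and Table 6). Section 3.10 says in general terms that early termination led to considerable changes.

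**The concern.** The protocol gives laboratory toxicity two routes into the report. One is adverse event reporting, which depends on the investigator's judgement. The other is a grade computed from the measured value, which does not. The SAP keeps the first route and replaces the second with cut-off counts for three cell types.

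For every other parameter, a reader of the report could not say how many patients reached a given grade unless an investigator had recorded an event. By-visit means do not answer that question, because a few severe values can sit behind an ordinary mean. Out-of-range flags in a listing do not separate a trivial departure from a severe one. For a radioimmunoconjugate whose main toxicity is to the marrow, a count that does not depend on judgement is worth having, and the protocol asks for the grading that would supply it.

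**Working it through.** There is no power, alpha or event-count figure to reproduce. The check is a comparison of texts and a count of coverage.

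**1. Commitment against plan.**

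| Item | Protocol | SAP |
|---|---|---|
| CTCAE grade for laboratory values | Derived by program (13.4.5); repeated in 14.1.10 | Not derived |
| CTCAE grade for adverse events | Yes (14.1.10) | Yes (3.8.1, Table 6) |
| Record of changes | SAP will document them (14.1.5) | General statement; laboratory grading not named (3.10) |

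**2. Coverage of the count table.** SAP 3.9 lists 11 haematology items and 14 biochemistry items. Items with a patient count below a cut-off:
- haematology: 3 of 11 (neutrophils, platelets, lymphocytes);
- biochemistry: 0 of 14;
- either group with a CTCAE grade: 0 of 25.

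**3. Where a severe value would appear.**

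| Parameter | Adverse event tables | Patient count | By-visit summary | Listing |
|---|---|---|---|---|
| Neutrophils, platelets, lymphocytes | If reported | Yes | Yes | Flagged |
| Haemoglobin, white cells | If reported | No | Yes | Flagged |
| Creatinine, bilirubin, ALT, AST, ALP | If reported | No | Unclear | Flagged |

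The last row is unclear because Table 1 rules out biochemistry summaries while 3.9.1 plans them for every laboratory parameter. The two cannot both stand.

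**4. Are the uncovered parameters relevant?**
- *White cells.* Protocol Table 4-4 gives 30 Grade 3 and 4 Grade 4 leukopenia events in Part A; 30 is the largest Grade 3 count in that table. The table states no denominator. Table 4-3 gives 57 + 9 + 7 + 1 = 74 patients, and Protocol 4.4 also uses 74. If each patient is counted once at worst grade, Grade 3 or higher is (30 + 4)/74 = 45.9%. If the four Grade 4 patients are also among the 30, it is 30/74 = 40.5%.
- *Lymphocytes.* The same table gives 23/74 = 31.1% Grade 3 and 2/74 = 2.7% Grade 4. The SAP has a single cut-off of 0.2, and the documents do not say which grade this marks. If it is the Grade 4 limit, the larger Grade 3 group is not counted; if it is the Grade 3 limit, both groups are.
- *Haemoglobin.* Part B entry is at 9.0 g/dL or above, and Protocol 9.4 sets severe anaemia at below 8.0 g/dL, a margin of 1.0 g/dL.
- *Liver and kidney.* Protocol 4.8.7.4 places both among the organs with the highest absorbed dose, though well below tolerance levels. SAP 3.9 drops urea and BUN for quality reasons. Creatinine remains as a renal marker, without a count.

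**5. Do these figures show missed events?** No. Table 4-4 is a table of treatment-emergent adverse events, so its leukopenia and lymphopenia were captured by the adverse event route. Protocol 9.4 states transfusion for haemoglobin below 8.0 g/dL, and a value needing transfusion is an adverse event under 13.1.1. The figures show that the parameters matter. They do not show how many severe values go unreported, and the documents give no such number.

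**The case against.** A reader might infer that the protocol bars severe anaemia, leukopenia, and liver or renal changes from adverse event reporting, so that the report would understate toxicity. The documents do not support that. The exclusion reaches only abnormalities that need neither clinical intervention nor further investigation. Clinically significant or treated values are adverse events, and they enter the SAP's tables by preferred term and by CTCAE grade. Nor is biochemistry plainly left without summaries, since 3.9.1 says otherwise.

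It can also be said that this is an abbreviated close-out SAP for a terminated study. It counts the two toxicities that Protocol 4.7 names as the most common at Grade 3/4, neutropenia and thrombocytopenia, and adds lymphocytes. It covers one vendor's outputs only. The protocol promises grading, but no worst-grade or shift table.

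Most of this stands and limits the point. It does not remove it. Early termination can justify a shorter plan, but Protocol 14.1.5 still asks that changes be documented. Section 3.10 mentions other sources for the report and gives the interim analysis as its instance; it names no source of laboratory grades. The protocol requires no particular table, but a grade that is derived and then not tabulated would leave the safety objective where it is now.

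**Conclusion.** The point holds in a limited form. Programmatic CTCAE grading of laboratory values is in the protocol, absent from the SAP and not named in 3.10. Patient counts exist for 3 of 25 listed laboratory items. For haemoglobin, white cells, liver tests and creatinine, incidence therefore rests on investigator reporting, supported by listings and by-visit summaries but by no objective count. Whether any severe value would go uncounted is unknown, and no size of under-counting can be given. The 45.9% leukopenia figure indicates relevance only; it assumes a denominator of 74 and one count per patient. This is a cheap improvement to the safety reporting, not a flaw that undermines the study's conclusions.

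**What to change.** - In SAP 3.9.1, derive the CTCAE grade by program for the gradable haematology parameters, including haemoglobin and white cells, and for creatinine, bilirubin, ALT, AST and ALP.
- Add one table of worst post-Betalutin grade by dose regimen. State its window (3.9.1 now stops at Day 92) and whether unscheduled results count; SAP 3.4 brings these in only for post-baseline maxima, which does not serve low values. A baseline-to-worst-grade shift table is optional.
- Reconcile Table 1 with 3.9.1 on whether biochemistry is summarised.
- Name in SAP 3.10 any remaining departure from Protocol 13.4.5, with the reason.

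The cost is SAP wording, a grading derivation and one table on data already collected and listed. The downside is a small amount of extra programming in a plan meant to be short.

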	(Within 4 weeks before 1st rituximab dose)	W2 prior to dosing	Day -1 or Dosing Day before adm (±2 day)	Dosing Day after adm	W1 (±2 day)	W3 (±2 days)	W4 (±2 days)	W5, 6,7,9,10,11 ⁶ (±2 days)	W8 (±3 days)	W12 (±7 days)	W26 (±7 days)	W 39 (±7 days)	W52 (±7 days)	Hospital visit every 6 months (±7 days)
Genomic biomarkers (DNA, RNA and proteins) in tumour tissue	(X) ¹⁰										(X) ¹⁰			
HLA haplotyping in blood	(X) ¹¹													
Bone marrow biopsy	X ⁵									X ⁵	X ⁵			
CT neck, thorax, abdomen, pelvis with contrast or MRI	X									X	X	X	X	2X 2 nd year X yearly 3-5
FDG PET/CT images	X									X	X			
ECG	X													
QoL (FACT-LYM) (Part B only)	X									X			X	
Adverse events	X	X	X	X	X	X	X	X	X	X				
Adverse Drug reaction											X	X	X	8X
SAE	X	X	X	X	X	X	X	X	X	X				
SAE related to treatment											X	X	X	8X
AEs of special interest											X	X	X	8X
Survival Status											X	X	X	8X

- 1) 5 years or until further anticancer therapy is given
 - 2) On the dosing day, within 4 hrs prior to Betalutin administration
 - 3) CD37 expression is assessed by immunohistochemistry using an archived tissue biopsy (FFPE block age <5 years. If block age 2-5 years, discuss with Sponsor) at screening, or if not available, a new tissue biopsy needs to be collected at screening. Repeat at relapse and/or disease progression (optional). The tumour biopsy sample(s) can be used for genomic biomarkers analysis if separate informed consent is given (see note 10).
 - 4) When patient is biopsied at relapse, CD37 expression should be assessed. Tumour biopsy at relapse is optional.
 - 5) At screening: The Bone Marrow Biopsy taken up to 8 weeks before rituximab administration may be used. At Complete Response: Bone marrow biopsy required for confirmation of CR if patient had bone marrow infiltration at baseline, otherwise it is optional.
 - 6) Blood samples weekly until platelet counts ≥ 100 x 10⁹/L and neutrophil counts (ANC) ≥ 1.5 x 10⁹/L after nadir values (these do not require a hospital visit).
 - 7) If the patient receives cancer related treatment, they should continue with limited long term follow-up and record the first course of cancer related treatment.
 - 8) Only if ADA test is positive at month 12. Blood samples to be collected at each visit until ADA-negative result.
 - 9) ADA immunogenicity blood sample to be taken before lilotomab dose

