Bone marrow biopsy	Bone marrow biopsy required for confirmation of CR if patient had BM infiltration at baseline
QoL	Part A Phase IIa only: FACT-Lym to be completed by the patient

9.6.2.4 Part B and Part C Day 7 to Month 3

Assessment or Procedure	Explanation
Week 1	
(S)AE	Any (S)AE since last visit should be recorded
Haematology	Including haematocrit, haemoglobin, platelet count, erythrocyte count, white blood cell count and differential (absolute count of neutrophils, lymphocytes, monocytes, eosinophils, basophils)
Biochemistry	Including sodium, potassium, calcium, creatinine, uric acid, BUN, ALP, ASAT, ALAT, LDH, gamma glutamyl transferase, glucose, total bilirubin, albumin
Immunogenicity	
 To monitor the ADA response. Serum samples to be sent to CCLS for biobanking.
Week 3, 5, 6, 7, 9, 10, 11	
The purpose of these visits is to take additional weekly blood samples after Betalutin administration (until platelet and ANC recovered to $\geq 100 \times 10^9/L$ and $\geq 1.5 \times 10^9/L$, respectively after nadir values. These samples can be taken remotely, except for patients having SPECT/CT and/or pharmacokinetic sampling (see Section 9.6.2.2) when a hospital visit is required on Day 21.	
(S)AE	Any (S)AE since last visit should be recorded
Haematology	Including haematocrit, haemoglobin, platelet count, erythrocyte count, white blood cell count and differential (absolute count of neutrophils, lymphocytes, monocytes, eosinophils, basophils)
Biochemistry	Including sodium, potassium, calcium, creatinine, uric acid, BUN, ALP, AST, ALT, LDH, gamma glutamyl transferase, glucose, total bilirubin, albumin
Week 4	
(S)AE	Any (S)AE since last visit should be recorded
Concomitant medication	Recording of concomitant medication used since last visit
Physical examination	Check and describe heart, lung and other significant findings
Vital signs	Pulse rate, blood pressure, body temperature
Pregnancy test (if applicable)	Urine dip stick
Haematology	Including haematocrit, haemoglobin, platelet count, erythrocyte count, white blood cell count and differential (absolute count of neutrophils, lymphocytes, monocytes, eosinophils, basophils)
Biochemistry	Including sodium, potassium, calcium, creatinine, uric acid, BUN, ALP, ASAT, ALAT, LDH, gamma glutamyl transferase, glucose, total bilirubin, albumin
Performance status	WHO PS

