2.1.1 Visit Structure

The visit structure and the schedule of assessments are detailed in Tables 6-7, 6-8 and 6-9 in the study protocol (Section 6).

In the protocol, the Betalutin administration day is referred to as Day 0. However, for statistical analysis and to be in line with CDISC (Clinical Data Interchange Standards Consortium) requirement, the Betalutin administration day will be defined as study Day 1. See Section 3.3 for more details.

The study treatment period starts with the single dose infusion of rituximab (375mg/m²) 14 days prior to the administration of Betalutin and lasts for 12 weeks after the Betalutin administration for each participant.

The follow-up period starts from 12 weeks (3 months or 92 days) after the first lilotomab/Betalutin administration up to 5 years as follows (see Protocol Section 6.3 Schedule of Assessments for more details):

- Extensive follow-up (hospital visits): for all participants, every 3 months after Betalutin administration for the first year (i.e. Month 3, Month 6, Month 9, and Month 12). In addition, there will be an additional hospital visit at Week 4 and Month 2 after Betalutin administration. Tumour imaging assessments are only required until the participant has disease progression as confirmed by the IRC or further anticancer therapy prior to progression. All other scheduled assessments are performed regardless of disease progression or administration of further therapy.
- After Month 12: follow-up will continue every 6 months up to 5 years after the Betalutin dose.
 - Extensive follow-up (hospital visits) will be performed until the participant has disease progression as assessed by the IRC or further anticancer therapy prior to progression.
 - Survival Follow-up: Thereafter, the participant will continue limited follow up every 6 months for potential long-term toxicity (new onset of Adverse Events of Special Interest (AESIs), Adverse Drug Reactions (ADRs) and study treatment-related Serious Adverse Events (SAEs), Overall Survival, further anticancer treatment and immunogenicity assessment (ADA, if applicable). Unless blood sampling is required for immunogenicity, limited follow-up visits can be performed by telephone.

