A visit window of ± 2 days is permitted for the nominal Day 0 visit (the dose of radioactivity will be based on the actual administration date). Weekly assessments should occur within a window of ± 2 days. Visits occurring at 4-week intervals will have a window of ± 3 days. During the treatment and follow-up period, a window of ± 7 days for visits occurring every 3 or 6 months is acceptable.

All samples/assessments for study baseline are to be obtained before rituximab dosing. The associated results will be used for Betalutin treatment baseline except for haematology, which is to be repeated within 72 hours prior to Betalutin administration and will be used as the Betalutin baseline.

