3.4 Data Presentation

The TFLs will present the dose regimens (where relevant) as detailed below:

Table 4: LYMRIT-37-01 study, Part B/C Treatment Group Descriptors

Order	Descriptor for Dose Regime (where relevant) to be presented in TFLs	Meaning of Descriptor
1 [1]	40 / 12.5	40 mg lilotomab plus 12.5 MBq/kg Betalutin
2	40 / 15	40 mg lilotomab plus 15 MBq/kg Betalutin
3	100 / 20	100 mg/m ² lilotomab plus 20 MBq/kg Betalutin
4 [1]	Received Rituximab only	Received Rituximab only
5 [1]	Enrolled no treatment	Enrolled but did not receive any trial treatment
6 [1]	Screen failure	Participants in the screened set who failed screening (i.e. are not eligible to join the study per the eligibility eCRF page).

[1] In table summaries, if there is insufficient space to present all treatment groups on a single page, these dose regimens will be presented on the next page.

The data will be summarised in tabular form by Study Part (i.e. B / C) and dose regimen.

Results from scheduled visits will be tabulated. Unscheduled visits will be included in assessments of maximum post-baseline. All assessments will be listed.

Table 5: Populations to be used for output

Type of data	Listings	Summaries
Disposition	Screened set	Screened set
Demographic characteristics and baseline	SAF	SAF, Efficacy Analysis Set
Efficacy	SAF	Efficacy Analysis set

AE's and lab data	SAF	SAF
-------------------	-----	-----

Listings will be sorted by Study Part (i.e. B / C) and dose regimen, patient number and date/time of assessment.

Graphical presentations of the data will also be provided where appropriate.

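### Weekly counts stop once they recover, so any mean neutrophil or platelet value shown for Weeks 9–11 would generally be too low; plot Week 12 after Week 8 and print the number sampled

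*SAP*

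**What the plan says.** Protocol Table 6-8 puts Weeks 5, 6, 7, 9, 10 and 11 in one column. Its note 6 makes those draws conditional: "Blood samples weekly until platelet counts" are at least 100 ×10⁹/L and neutrophils (ANC) at least 1.5 ×10⁹/L after the nadir. Section 9.6.2.4 repeats the condition: "The purpose of these visits is to take additional weekly blood samples after Betalutin administration (until platelet and ANC recovered to" the same two limits. Weeks 8 and 12 have their own columns, where haematology does not carry that note.

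On the analysis side, SAP 2.1.1 takes its visits from the protocol: "The visit structure and the schedule of assessments are detailed in Tables 6-7, 6-8 and 6-9 in the study protocol". SAP 3.4 adds "Results from scheduled visits will be tabulated". SAP 3.9.1 asks for values at each scheduled visit and for "Change from Betalutin baseline at each post-baseline analysis window (scheduled visit) for all laboratory parameters". It also asks for the mean plots: "Mean haematological data, for each dose regimen, will be plotted for neutrophil count, platelet counts, lymphocytes". The only time limit is "Only data from day 0/1 to day 92 will be included in any summary tables and plots". Nothing in SAP 3.9.1 mentions the stop at recovery, and Protocol 14.1.12 rules out imputation, so the means rest on whoever was drawn.

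**The concern.** Leaving the weekly sample is decided by the very counts being averaged. A patient drops out of Weeks 9–11 because both lines have recovered, then returns at Week 12 with everyone else. An observed-only mean in that stretch is therefore selected on the outcome. The plotted curve would lie too low late on and then step up at Week 12 for reasons unrelated to the marrow. Protocol 4.7 describes the cytopenias as generally transient, and these plots are where a reader of the close-out report would look for the time course in Parts B and C.

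**Working it through.** The plan gives no figure to reproduce here. The check has five steps.

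**1. When the stop takes effect.** Protocol 4.7 gives nadirs at Day 40 (range 34–43) for platelets and Day 49 (range 43–56) for neutrophils. Week 6 is Day 42, before the earliest reported neutrophil nadir, so both counts can first be past nadir at Week 7 (Day 49). Week 8 is drawn for all. The first draw that can be skipped is Week 9. Weeks 5–7 are near complete only if those ranges hold for individual patients; the sentence speaks of mean nadirs, so this is not certain.

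**2. Are Week 9–11 means produced?**
- For: SAP 2.1.1, 3.4 and 3.9.1 work by scheduled visit, and Table 6-8 schedules haematology at Weeks 9–11.
- Against: SAP Table 3, introduced for laboratory outputs, has windows for Week 8, Week 12, Month 3 and two cumulative periods only. But it also has none for Weeks 1 and 3–7, so read as the full list it would leave the nadir off the plot.

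Production is likely but not stated.

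**3. Direction.** With a fraction f still sampled, mean(all) = f × mean(sampled) + (1 − f) × mean(recovered), so

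bias = (1 − f) × [mean(sampled) − mean(recovered)].

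This is negative whenever recovered patients have the higher mean on that line.

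**4. Size, illustrative.** Nadirs are lognormal, fitted to Protocol Table 4-5 (40/15, n = 36).
- ANC below 1 in 20/36 (z = 0.140) and below 0.5 in 7/36 (z = −0.862): log-SD = ln 2 / (0.140 + 0.862) = 0.69; median = exp(−0.140 × 0.69) = 0.91.
- Platelets below 50 in 20/36 and below 25 in 6/36 (z = −0.967): log-SD = ln 2 / (0.140 + 0.967) = 0.63; median = 50 × exp(−0.140 × 0.63) = 46.

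Assumed, not in the documents: median baseline ANC 3.5 (log-SD 0.35, floor 1.5) and platelets 210 (log-SD 0.25, floor 150); linear recovery over 28–56 days to 75% of baseline; ANC–platelet correlation 0.5; every recovered patient stops. At Week 11 about 35% are still sampled, and plotted ANC is 1.64 against 2.25 for all. The recovered mean is then (2.25 − 0.35 × 1.64)/0.65 = 2.58 and the bias 0.65 × (1.64 − 2.58) = −0.61, or −27%; coding choices move this to about −24%. Week 12 ANC is 2.50, so the plotted rise is 2.50 − 1.64 = 0.86 against a true 2.50 − 2.25 = 0.25.

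Bias at Weeks 9 / 10 / 11 when assumptions change:

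| Setting | ANC | Platelets |
|---|---|---|
| Example above | −11 / −17 / −25% | −6 / −8 / −9% |
| Median of 648 settings, all stop | −12 / −20 / −26% | −4 / −6 / −7% |
| Exponential-type recovery, half-time 14 days | −17 / −24 / −30% | −11 / −16 / −20% |
| ANC recovers in 14–28 days, platelets in 42–84 | −5 / −4 / −4% | −9 / −15 / −21% |

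The 648 settings vary recovery shape and time, visit noise, plateau, baseline ANC and correlation. In them the median share still sampled at Week 11 is 24% (10th–90th percentile 3–62%). If three quarters of recovered patients stop, the median Week 11 ANC bias is 10% (3–13); if half stop, 5% (1–7). Weeks 8 and 12 show no bias in any run.

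**5. Month 3 overlap.** An on-time Week 11 draw is 77 + 1 = SAP Day 78, the first day of the Month 3 window (Days 78–122), which also holds the Week 12 draw. With ±2 days allowed, three of the five possible days (78, 79, 80) fall inside, and no rule picks one count. Taking the first lowers mean ANC by 0.7% (range 0–6).

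**The case against.** The faulty output is inferred. SAP 3.9.1 ties its summaries to analysis windows, and Table 3 has none for Weeks 9 or 10. SAP 3.1 refers to a shells document, not available here, which could settle the plotted visits. This stands, and is why the point is conditional.

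The sizes rest on assumptions. The nadirs come from Part A Arm 1, which had a different rituximab schedule and only 25 FL patients among 36. Sites may keep drawing, since Protocol 6.3 permits extra examinations. This also stands: the percentages are illustrations.

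A reader might infer that neutrophils are always the worse affected, given their later nadir. The fourth row of the table reverses that order. Protocol 9.4 also prescribes G-CSF for persistent neutropenia; with full G-CSF use, slow platelet recovery and positive correlation, the ANC bias vanishes or turns slightly positive (0 to +4%).

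The harm is limited. Any error usually overstates toxicity, SAP 3.1 gives n in the tables, and the claim in Protocol 4.7 concerns recovery by 3 months, for which the Week 12 draw is complete. What remains is a late curve that misleads the eye, because nothing requires n on the plots.

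**Conclusion.** The point holds as a minor one. If Week 9–11 means are shown, they are selected on the outcome and will generally be too low for both lines, with an artificial rise at Week 12. The plausible size is roughly 5–25% or more for ANC and a few percent to about 20% for platelets. It depends on recovery speed, G-CSF use and adherence to the stop; the sign fails only in extreme settings.

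Two stronger readings are not supported. One is that the plots would reverse the order of the regimens. Comparing 14–28-day with 28–56-day recovery, ANC order reversed in 0, 39 and 107 of 162 pairs at Weeks 9, 10 and 11 when every recovered patient stopped, and in none when a quarter or more kept being drawn. No between-regimen test is planned, and 100/20 had already been dropped. The other is that the safety conclusions are compromised: the ever-below-threshold counts, adverse event grades, listings and Week 12 values do not depend on the late weekly draws.

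**What to change.** In SAP 3.9.1, state that after Week 8 the by-visit summaries and mean plots show Week 12 only, with Week 9–11 counts kept in the listings. Print the number sampled under every plotted visit, including Weeks 5–7, so that any early stopping there is visible. In SAP Table 3, state that when two counts fall in one window the one nearest the target day is used.

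The cost is three fewer plotted points and a few sentences in the SAP. Conduct, dosing and supportive care do not change.
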